**Table 2 Schedule of Assessments**

	Screening a	Part A										Part B			EOS k	Un-Scheduled k
Week		Baseline b	0	1	2	2	4	8	12	16	20	24 j	26	36	52	
Visit	1	2	3	4	5	6	7	8	9	10	11	12	13	14	15	
Day (± window in days)	-30 (within -60) a	1	3	8	15 ±1	17 ±1	29 ±3	57 ±3	85 ±3	113 ±3	141 ±3	169 ±3	183 ±3	253 ±7	365 ±7	
Assessments																
Informed consent	X															
Inclusion/exclusion criteria	X	X c														
Demography	X															
Medical/surgical history	X															
Physical examination d	X	X	X	X	X	X	X	X	X	X	X	X	X	X	X	X
Neurological examination e	X	X	X	X	X	X	X	X	X	X	X	X	X	X	X	X
Vital signs f	X	X			X							X	X		X	X
Chest X-ray g	X															X s
Resting 12-ECG h	X														X	X
AEs/Serious AEs/ADRs		X	X	X	X	X	X	X	X	X	X	X	X	X	X	X
Prior/concomitant medication	X	X	X	X	X	X	X	X	X	X	X	X	X	X	X	X
Urine or serum pregnancy test i	X	X			X							X	X		X	X
Study drug																
Contact IXRS	X	X			X							X l	X l		X	
Randomization		X										X				
Drug infusion m		X			X							X	X			

	Screening a	Part A										Part B			EOS k	Un-Scheduled k
Week		Baseline b	0	1	2	2	4	8	12	16	20	24 i	26	36	52	
Visit	1	2	3	4	5	6	7	8	9	10	11	12	13	14	15	
Day (± window in days)	-30 (within -60) a	1	3	8	15 ±1	17 ±1	29 ±3	57 ±3	85 ±3	113 ±3	141 ±3	169 ±3	183 ±3	253 ±7	365 ±7	
Efficacy assessments																
HAQ-DI, including Patient's pain VAS n		X						X		X		X		X	X	
Patient Global Assessment VAS n		X						X		X		X		X	X	
Physician Global Assessment VAS		X						X		X		X		X	X	
Swollen and tender joint counts o		X						X		X		X		X	X	
Laboratory assessments																
Virology screening p	X	X					X	X	X	X	X	X		X	X	X
QuantiFERON ® -TB Gold q	X															X
IgG, IgM, IgA	X r							X		X		X		X	X	
CRP / ESR	X	X						X		X		X		X	X	
RF	X															X
Clinical chemistry, hematology and urinalysis	X	X			X		X	X	X	X	X	X		X	X	X
PK sampling s		X	X	X	X	X	X	X	X	X	X	X				X
PD (CD19+ B-cell) sampling s		X	X	X	X	X	X	X	X	X	X	X		X	X	X
Immunogenicity sampling t		X		X	X		X		X	X		X		X	X	

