### 3.6.1.2 Study Drug Administration Part A

Prior to Day 1, patients will be discontinued from their current anti-TNF medication, other biologic DMARDs or non-biologic DMARDs, except MTX.

The following must be performed on **Baseline (Day 1, Week 0)**:

Review inclusion and exclusion criteria and confirm patient eligibility. If eligible, the following procedures should be performed:

- Physical examination and vital signs;
- Neurological examination;
- Documentation of concomitant medications;
- Assessment of AEs/SAEs/ADRs;
- Urine pregnancy test for applicable female;
- Randomization to one of the study drugs;
- Contact IXRS.

The following efficacy assessments will be performed:

- Patient's assessment: global VAS and HAQ-DI, including patient's pain VAS;
- Physician's assessment: global VAS;
- Joint assessment. Each of the 66/68 joints will be evaluated for tenderness and swelling.

The following laboratory assessments will be performed:

- Clinical chemistry, hematology, urinalysis and HBV DNA only when negative HBsAg and positive HbcAb at screening;
- CRP, ESR;
- PK and PD sample collection;
- Immunogenicity.

The following must be also performed:

- The first of the two infusions of the study drug, as per IXRS.

The following must be performed on **Day 3 (Week 0)**:

- Physical / Neurological examination;
- Documentation of concomitant medications;
- Assessment of AEs/SAEs/ADRs;
- PK and PD sample collection.

The following must be performed on **Day 8 (Week 1)**:

- Physical / Neurological examination;
- Documentation of concomitant medications;
- Assessment of AEs/SAEs/ADRs;
- PK and PD sample collection;
- Immunogenicity.

The following must be performed on **Day 15 ± 1 day (Week 2)**:

- Physical examination and vital signs;
- Neurological examination;
- Documentation of concomitant medications;
- Assessment of AEs/SAEs/ADRs;
- Urine pregnancy test for applicable female;
- Contact IXRS;
- The second of the two infusions of study drug, as per IXRS;
- Clinical chemistry, hematology, urinalysis
- PK and PD sample collection;

- Immunogenicity.

The following must be performed on **Day 17 ± 1 day (Week 2)**:

- Physical / Neurological examination;
- Documentation of concomitant medications;
- Assessment of AEs/SAEs/ADRs;
- PK and PD sample collection.

The following must be performed on **Day 29 ± 3 days (Week 4)**:

- Physical / Neurological examination;
- Documentation of concomitant medications;
- Assessment of AEs/SAEs/ADRs.

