**Table 3 Clinical Laboratory Assessments**

Hematology	White blood cell count, red blood cell count, hemoglobin, platelets, absolute neutrophil count
Clinical chemistry (serum)	Creatinine, aspartate transaminase, alanine transaminase (ALT), lactate dehydrogenase, alkaline phosphatase (ALP), total bilirubin, cholesterol, calcium, glucose, gamma glutamyl transferase (GGT), phosphate, hCG
Urinalysis	Glucose, blood, protein, hCG
Virology	Hepatitis C virus antibodies, human immunodeficiency virus, hepatitis B surface antigen, and hepatitis B core antibody (total and immunoglobulin M), HBV DNA
Other	C-reactive protein, rheumatoid factor, erythrocyte sedimentation rate*, QuantiFERON-TB Gold

\* ESR estimation (Westergren method) and urine pregnancy test would be performed locally

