## **5.7 Changes in Clinical Laboratory Assessment Results**

It is the responsibility of the Investigator or Sub-investigator to review the results of all laboratory tests as they become available. For each abnormal laboratory test result, the Investigator or Sub-investigator needs to ascertain if this is an abnormal (i.e., clinically significant) change from Baseline for that individual patient. This determination, however, does not necessarily need to be made the first time an abnormal value is observed. The Investigator or Sub-investigator may repeat the laboratory test or conduct additional tests to verify the results of the original clinical laboratory tests. If this laboratory value is determined by the Investigator or Sub-investigator to be a clinically significant change from Baseline for that patient, it is considered to be an AE.

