### 3.1. DATA AND SAFETY MONITORING BOARD (DSMB)

There will be at least 3 DSMB meetings for reviewing safety data in this study. Analysis for first and second DSMB meetings will be described in a separate DSMB SAP; while the third (all patients at week 26) and onward will be based on this SAP where analyses described in section 8-12 and 16 will be performed. Other analyses may be added in case they are thought to affect DSMB safety review, however no statistical inference will be included in order to avoid an inflation of the type I error.

The first DSMB analysis will be considered as Interim Analysis of 10 patients per group (30 patients in total) of safety data collected up to Week 4 whose safety report will be submitted to regulatory. For additional details on DSMB meetings, please refer to the DSMB charter dated 26Jan2017.

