### Drug-Induced Liver Injury (DILI)

Drug-induced liver injury will be assessed through the number of possible Hy's law cases as following:

---

Document:	\\eedc-vnasc01\Biosdata\Archigen\SAIT101\YWA21301\Biostatistics\Documentation\SAP	Version Number:	V2.0
Author:		Version Date:	13Feb2019
Template No:	CS_TP_BS016 Revision 4	Reference:	CS_WI_BS005
Effective Date:	01Apr2016		

- ALT or AST > 3 × ULN, and
- ALP < 2 × ULN, and
- Total bilirubin ≥ 2 × ULN

All parameters above should be measured at the same visit. The possible Hy's law cases will be summarized and listed by treatment groups.

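### The SAP's Hy's law count pairs results only within a visit, so an episode whose transaminase and bilirubin limits are never met together at one visit is missed

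*SAP*

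**What the plan says.** SAP 16.2, under Drug-Induced Liver Injury, assesses liver injury by the number of possible Hy's law cases. The conditions are "ALT or AST > 3 × ULN, and" ALP below 2 × ULN, together with "Total bilirubin ≥ 2 × ULN". It then states "All parameters above should be measured at the same visit". Strictly, that sentence is about when the parameters are measured. The natural reading is that all three limits must be met on results from one visit, and no pairing across visits is described. Cases are to be summarized and listed by treatment group.

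All four analytes belong to one chemistry panel: Protocol Table 3 lists "Creatinine, aspartate transaminase, alanine transaminase (ALT), lactate dehydrogenase, alkaline phosphatase (ALP), total bilirubin" among its contents. In Protocol Table 2 the row "Clinical chemistry, hematology and urinalysis" is marked at screening, Day 1, Day 15, Weeks 4, 8, 12, 16, 20, 24, 36 and 52, and in the unscheduled column. It is not marked at Week 26.

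Protocol 5.7 says that, after an abnormal result, the investigator "may repeat the laboratory test or conduct additional tests to verify the results of the original clinical laboratory tests". It gives no timing and does not say to which visit such a test belongs. SAP 5.3 leaves unscheduled results out of by-visit summaries. Where a retest keeps the same visit number, it uses the latest value for them. Neither section says what happens in the Hy's law count.

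For the third DSMB meeting onward, SAP 3.1 says that "analyses described in section 8-12 and 16 will be performed", which includes this count.

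**The concern.** Transaminases and bilirubin need not peak together. If ALT has dropped below its limit by the time bilirubin reaches its own, and no blood draw falls in any period of overlap, the same-visit rule returns no case.

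This is the only planned output that combines the liver parameters. The other outputs in SAP 16.2 work one parameter at a time, and the listings flag values as high or low against the normal range, not as multiples of ULN. A reader of the tables, including the DSMB, could see zero possible cases when a staggered episode had occurred, and would have to rebuild it by hand from the listings. The setting makes a sensitive screen reasonable: methotrexate is required background treatment (Protocol 3.4.2), hepatitis reactivation is an adverse event of special interest (Protocol 5.4), and some patients with evidence of prior hepatitis B may enrol (Protocol 3.2.7).

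**Working it through.** The plan states no figure of its own here, so there is none to reproduce.

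**Step 1: spacing of scheduled chemistry (Protocol Table 2).** The nominal days are 1, 15, 29, 57, 85, 113, 141, 169, 253 and 365. The visit windows are 0, ±1, then ±3 for Days 29 to 169, and ±7 for Days 253 and 365. The gap is the difference in nominal days; its range adds or subtracts both windows.

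| Interval | Nominal gap | Range |
|---|---|---|
| Day 1 to 15 | 14 days | 13 to 15 |
| Day 15 to 29 | 14 days | 10 to 18 |
| Day 29 to 169 (five gaps) | 28 days each | 28 ± (3 + 3) = 22 to 34 |
| Day 169 to 253 | 84 days | 84 ± (3 + 7) = 74 to 94 |
| Day 253 to 365 | 112 days | 112 ± (7 + 7) = 98 to 126 |

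Spacing is thus 2 to 16 weeks overall, and 4 to 16 weeks after Week 4. With no panel at Week 26, the first scheduled panel after the Week 24 infusion is 84 days later.

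**Step 2: a patient who is not counted.** At one visit ALT is 5 × ULN and bilirubin 1.5 × ULN. At the next, ALT is 2.8 × ULN and bilirubin 3 × ULN. ALP is normal throughout. The first visit fails on bilirubin and the second on ALT, so there is no case.

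**Step 3: retests.** If the latest-value rule in SAP 5.3 were carried over to this count, an ALT retest under the same visit number that had fallen below 3 × ULN would replace the qualifying value. The SAP does not say whether it is carried over.

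**Step 4: how much a window could add.** The documents give no durations or lags, so these are assumptions. ALT is above its limit for D days from day 0, bilirubin for D days from day L, and ALP stays below its limit. Visits are exactly 28 days apart, and the first visit falls at u, uniform from 0 to 28.

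- Same visit: u must lie between L and D, so capture = (D − L)/28.
- A window that spans one interval but not two (31 and 35 days behave alike on this exact grid) also captures ALT at u with bilirubin at u + 28. That needs u ≤ L + D − 28, so added capture = (L + D − 28)/28.

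| D | L | Same visit | Added | With window |
|---|---|---|---|---|
| 21 | 7 | 14/28 = 50% | 0/28 = 0 | 50% |
| 21 | 14 | 7/28 = 25% | 7/28 = 25 points | 50% |
| 21 | 21 | 0/28 = 0% | 14/28 = 50 points | 50% |
| 28 | 14 | 14/28 = 50% | 14/28 = 50 points | 100% |

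Now add a full repeat panel 10 days after a high ALT, with D = 21 and L = 14. The same-visit rule succeeds for u from 14 to 21, or from 4 to 11 through the repeat: (7 + 7)/28 = 50%. With the window, bilirubin is found at u (14 to 21), at u + 10 (u from 4 to 21) or at u + 28 (u up to 7). Together these cover u from 0 to 21: 21/28 = 75%.

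**Step 5: the long gaps.** The shortest possible Week 24 to 36 interval is 74 days and the shortest Week 36 to 52 interval is 98 days. A window of about 35 days spans neither, so scheduled visits alone gain nothing there.

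**The case against.** The strongest case against is that little is hidden and nothing inferential depends on the count. All laboratory values are listed with flags, and shift tables and abnormality incidences are produced; these fall under the same DSMB scope as the Hy's law count. A clinically significant laboratory change is an adverse event (Protocol 5.7), hepatitis reactivation is reported on expedited timelines, and SAP 16 makes no between-group safety comparisons. An unscheduled panel contains all four analytes and can qualify by itself. In the example above, a repeat raises same-visit capture from 25% to 50%, so follow-up testing partly cures the problem. All of this stands, and it keeps the point small. It does not supply a combined count that recognises staggered results.

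A reader might also infer more than the documents support:

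- That chemistry is never closer than 4 weeks. It is 2 weeks apart between Days 1, 15 and 29.
- That any episode spread over two visits is lost. It is counted if all limits are met at either visit.
- That follow-up tests always fall at another visit. Protocol 5.7 does not assign them, and SAP 5.3 allows retests under the same visit number.
- That a later ALP rise removes a case. A patient who has met all limits at one visit remains a case. ALP leads to a miss only when it is already at or above 2 × ULN at the visit where the other two limits are first met together, and no later visit meets all three.

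**Conclusion.** The gap is real but narrow. On the natural reading of SAP 16.2, an episode whose transaminase and bilirubin limits are never met at one visit is left out of the only planned combined liver-injury count. The treatment of unscheduled and repeat results in that count is also unstated.

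In the five scenarios worked above, the gain from a cross-visit window runs from none to 50 percentage points of capture at 28-day spacing. That range rests wholly on assumed durations and lags. The documents give no expected number of cases, so the effect in this trial cannot be stated. The output is descriptive and individual values remain in the listings; no PK or efficacy conclusion is touched. The inference that liver injury would go unseen is not supported. What can be said is that one summary row may read zero when the listings contain a staggered episode. This is a worthwhile, minor improvement.

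**What to change.** Keep the same-visit count and add one descriptive row to the table in SAP 16.2:

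- **Pairing.** ALT or AST above 3 × ULN, followed on the same day or within a stated window by total bilirubin of at least 2 × ULN.
- **Window.** Long enough for one 4-week interval with its visit windows. That can reach 34 days, so 35 days would serve. A 30- or 31-day window would lose some consecutive visits.
- **ALP.** Below 2 × ULN at the time of the transaminase elevation.
- **Data used.** All dated results, whether scheduled, unscheduled or repeat. State that the latest-value rule in SAP 5.3 does not apply here, so that a same-visit retest cannot overwrite a qualifying value.

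The cost is a few lines of SAP text and one derivation. The downside is a few extra candidate cases to list and review. At the 12- and 16-week gaps, any gain comes only from unscheduled tests. The change adds no visit or sample and does not affect patient management.

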### 16.3. 12-LEAD ECG EVALUATION

The following summaries will be provided for ECG data:

Incidence of ECG evaluation results by visit

Listing of all ECG evaluation results.

### 16.4. VITAL SIGNS

The following vital signs measurements will be reported for this study:

- Systolic blood pressure (mmHg)
- Diastolic blood pressure (mmHg)
- Pulse (beats/min)
- Body Temperature (°C)
- Respiratory Rate (breaths/min)
- Weight (kg)

The following summaries will be provided for vital signs and weight data:

- Actual and change from baseline by visit
- Shift table of incidence of abnormal values (abnormal low, normal, abnormal high), based on pre-defined abnormalities criteria, from baseline to each post-baseline visit
- Overall abnormalities incidence result will be summarized, and further break down by high/low abnormalities. Patients will be counted at most once for a high or low abnormality for each laboratory parameter.
- Overall abnormalities from Day 1: Patients with at least one abnormal (abnormal high or abnormal low) result up to Week 24, 52 after Day 1 will be considered as overall abnormal; Otherwise, patient without any abnormal result up to Week 24, 52 after Day 1 will be considered as overall normal.

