### **6.6.4 Vital Signs, ECG Findings, and Physical Examination**

Summary statistics will be presented for results at each visit with vital sign assessments and at End-of-Study, as well as for change from Baseline results to each visit with vital sign assessments and End-of-Study for systolic and diastolic blood pressure, and pulse rate.

The overall incidence of vital sign abnormalities will also be presented. Patients will be counted at most once for an abnormality for each vital sign parameter.

A listing of all vital sign abnormalities will be presented for the safety set. Criteria used to define abnormal vital sign results will be defined in the SAP. Shifts (abnormal low, normal, and abnormal high) for changes from Baseline to each post-baseline visit with vital sign assessments and End-of-Study, based on normal ranges, will be presented for vital sign parameters.

A table and listing of any ECG abnormalities at Screening will be presented for the Safety Analysis Set.

A listing of physical examination abnormalities will be presented for the Safety Analysis Set.

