#### Vital Signs Clinically Significant Abnormal Criteria

Clinically significant abnormal quantitative vital signs measurements will be identified in accordance with the following clinically significant abnormal criteria:

---

Document: \\ieedc-vnasc01\Biosdata\Archigen\SAIT101\YWA21301\Biostatistics\Documentation\SAP  
Author:

Version Number: V2.0  
Version Date: 13Feb2019

Template No: CS\_TP\_BS016 Revision 4  
Effective Date: 01Apr2016

Reference: CS\_WI\_BS005

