**Table: Clinically Significant Abnormal Criteria of Vital Signs**

Variable	Unit	Visit	Low	High
Systolic blood pressure	mmHg	Baseline	< 90 mmHg	> 180 mmHg
		Post-baseline	≤ 90 mmHg AND change from baseline ≤ -20 mmHg	≥ 180 mmHg AND change from baseline ≥ 20 mmHg
Diastolic blood pressure	mmHg	Baseline	< 50 mmHg	> 110 mmHg
		Post-baseline	≤ 50 mmHg AND change from baseline ≤ -15 mmHg	≥ 105 mmHg AND change from baseline ≥ 15 mmHg
Pulse	beats/min	Baseline	< 50 beats/min	> 120 beats/min
		Post-baseline	≤ 50 beats/min AND change from baseline ≤ -15 beats/min	≥ 120 beats/min AND change from baseline ≥ 15 beats/min
Body temperature	°C	Baseline	< 35.0 °C	> 38.3 °C
		Post-baseline	≤ 35.0 °C AND change from baseline ≤ -1.1 °C	≥ 38.3 °C AND change from baseline ≥ 1.1 °C
Respiratory rate	breaths/min	Baseline	≤ 10 breaths/min	≥ 24 breaths/min
		Post-baseline	≤ 10 breaths/min	≥ 24 breaths/min
Weight	kg	Baseline	None	None
		Post-baseline	percentage change from baseline ≤ -7.0 %	percentage change from baseline ≥ 7.0 %

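### The SAP 16.4 shift table for blood pressure, pulse and temperature classifies baseline and post-baseline values by different rules, so a persisting abnormal value is shown as a shift to Normal

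*SAP*

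**What the plan says.** SAP 16.4 lists six measurements: systolic and diastolic blood pressure, pulse, temperature, respiratory rate and weight. Among the planned summaries is a "Shift table of incidence of abnormal values (abnormal low, normal, abnormal high), based on pre-defined abnormalities criteria, from baseline to each post-baseline visit".

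That bullet does not say where the criteria are. The section ends with one table of criteria, introduced by the sentence "Clinically significant abnormal quantitative vital signs measurements will be identified in accordance with the following clinically significant abnormal criteria". No other vital-sign limits appear in the SAP.

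The table has separate rows for baseline and post-baseline. At baseline, systolic pressure is Low below 90 and High above 180, with no further condition. After baseline, Low requires "≤ 90 mmHg AND change from baseline ≤ -20 mmHg" and High requires "≥ 180 mmHg AND change from baseline ≥ 20 mmHg". The other three affected parameters follow the same pattern on the high side: diastolic "≥ 105 mmHg AND change from baseline ≥ 15 mmHg", pulse "≥ 120 beats/min AND change from baseline ≥ 15 beats/min" and temperature "≥ 38.3 °C AND change from baseline ≥ 1.1 °C". Respiratory rate has identical limits at both times and no change condition. Weight has no baseline criterion and uses only a 7% change afterwards.

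Protocol 6.6.4 also plans vital-sign shifts and says that these, "based on normal ranges, will be presented for vital sign parameters". The sentence before it leaves the definition of abnormal vital-sign results to the SAP. SAP 2.6, which lists changes from the protocol, does not mention vital signs.

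**The concern.** A shift table cross-tabulates one classification at two times, so its off-diagonal cells mean something only if Low, Normal and High are defined alike on both axes. Here they are not. A patient outside the limits at baseline enters as High or Low on the value alone, but can stay there only by worsening further by the full change threshold. Otherwise the patient falls into Normal.

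The error has a direction: an unchanged or somewhat worse abnormality is displayed as resolved. Vital signs are a listed safety endpoint in protocol 2.3.5. A reader of the study report would take a High-to-Normal cell as normalization when the reading may have risen.

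**Working it through.** There is no stated figure to reproduce. The check is to apply the SAP 16.4 criteria literally.

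**Inputs and bounds.** Let b be the baseline value and p the later value. For a patient High at baseline, staying High needs p ≥ b + threshold, because b already exceeds the absolute limit. For a patient Low at baseline, staying Low needs p ≤ b − threshold.

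| Parameter | Baseline Low / High | Post-baseline Low | Post-baseline High | To stay High | To stay Low |
|---|---|---|---|---|---|
| Systolic (mmHg) | <90 / >180 | ≤90 and change ≤ −20 | ≥180 and change ≥ 20 | above 180 + 20 = 200 | below 90 − 20 = 70 |
| Diastolic (mmHg) | <50 / >110 | ≤50 and change ≤ −15 | ≥105 and change ≥ 15 | above 110 + 15 = 125 | below 50 − 15 = 35 |
| Pulse (beats/min) | <50 / >120 | ≤50 and change ≤ −15 | ≥120 and change ≥ 15 | above 120 + 15 = 135 | below 50 − 15 = 35 |
| Temperature (°C) | <35.0 / >38.3 | ≤35.0 and change ≤ −1.1 | ≥38.3 and change ≥ 1.1 | above 38.3 + 1.1 = 39.4 | below 35.0 − 1.1 = 33.9 |

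**Worked cases.**

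- Systolic 185 to 195: change +10, less than 20, so High to Normal. 185 to 204 (+19) is also High to Normal. 185 to 205 (+20) is the first value that stays High.
- Systolic 88 to 80: change −8, short of −20, so Low to Normal. 85 to 66 (−19) is Low to Normal; 85 to 65 (−20) stays Low.
- Diastolic 112 to 126: change +14, so High to Normal; 127 is needed to stay High.
- Pulse 48 to 45: change −3, so Low to Normal. 125 to 139 (+14) is High to Normal; 140 is needed to stay High.
- Temperature 38.5 to 39.5: change +1.0, so High to Normal; 39.6 is needed to stay High.
- Respiratory rate 26 to 26 is High to High and 9 to 9 is Low to Low, so there is no artefact.

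**Limits that differ.** A diastolic reading of 108 is Normal at baseline because it does not exceed 110. After baseline it passes the 105 limit and is High if the rise is at least 15, for example from 90 (+18). The strict inequalities for these four parameters at baseline also become non-strict afterwards.

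**With one rule on both axes.** Using the baseline limits at both times, 185 to 195 is High to High, 88 to 80 is Low to Low, 112 to 126 is High to High, 48 to 45 is Low to Low and 38.5 to 39.5 is High to High.

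**Comparison within the SAP.** The laboratory shift table in SAP 16.2 uses one reference range at both times. Respiratory rate in the vital-sign table does the same.

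**The case against.** The strongest reply is that the criteria do what their title says. They identify clinically significant abnormalities, and requiring a change as well as a limit is a sensible way to count new, marked events rather than pre-existing ones. On that view, systolic 172 to 188 (+16) staying Normal is the rule working as designed. This stands for an incidence count. It does not rescue a cross-tabulation whose other axis uses the limit alone.

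Second, a reader might infer an undeclared departure from the protocol. The documents support only a weaker statement. Protocol 6.6.4 does name normal ranges for the shifts, but it supplies none for vital signs and leaves the criteria for abnormal results to the SAP. The silence in SAP 2.6 is an omission worth repairing, not proof of a hidden change.

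Third, a reader might infer that infusion hypotension would be missed, since protocol 3.2.1 warns of it. The false shift concerns patients already outside the limits at baseline. A fall to 90 or below from a baseline of 110 or more is always flagged (110 − 90 = 20). Some falls from 90–109 are not. But protocol 3.6.5.4 has clinically relevant findings reported as adverse events, and infusion reactions are events of special interest with their own summary in SAP 16.1.

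Fourth, the table templates mentioned in SAP 7 are not available, and the shift-table bullet does not cite the criteria table. The link is the natural reading, since no other criteria exist, but it is inferred.

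**Conclusion.** The point holds for systolic pressure, diastolic pressure, pulse and temperature: four of the six measurements. Followed as written, the shift table shows persisting or modestly worsening abnormalities as normalization. It does not hold for respiratory rate. Weight has a different weakness: with no baseline category, its shift table is uninformative.

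The consequence is limited. The output is descriptive, SAP 16 plans no between-group comparison of safety data, and observed values and changes by visit are summarized alongside. No endpoint decision depends on it. The number of patients affected cannot be given, because the documents contain no baseline vital-sign distribution. It may be small: the entry criteria exclude active infection and unstable medical conditions, and vital signs are scheduled at only four visits after Day 1 (Day 15 and Weeks 24, 26 and 52).

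A reader might also conclude that the overall incidence of abnormalities is wrong. The documents do not settle which criteria feed that summary, and a limit-plus-change rule is defensible there.

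The conclusion assumes that the shift table uses the section 16.4 criteria, baseline row for baseline and post-baseline row for later visits.

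**What to change.** In SAP 16.4:

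- Define Low, Normal and High for the shift table by one set of absolute limits per parameter, applied at both times with the same inequalities, or by the normal ranges that protocol 6.6.4 names. If normal ranges are used, state them. Settle on one diastolic high limit.
- Keep the limit-plus-change criteria for a separately labelled summary of clinically significant post-baseline abnormalities.
- Take weight out of the shift table and report changes of 7% or more in either direction as incidence.
- Cite the criteria table explicitly in each bullet that uses it.

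If the sponsor prefers the current rule, enter it in SAP 2.6 and footnote the table to say that Normal after baseline includes values outside the limits that did not change by the threshold.

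The cost is SAP wording and table programming. No new data are needed.
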